##### **11.1.3.2 Progression free survival**

PFS (per RECIST 1.1 as assessed by the BICR) will be defined as the time from the date of randomisation until the date of objective disease progression or death (by any cause in the absence of progression) regardless of whether the patient withdraws from randomised therapy or receives another anti-cancer therapy prior to progression. Patients who have not progressed or died at the time of analysis will be censored at the time of the latest date of assessment from their last evaluable RECIST 1.1 assessment. However, if the patient progresses or dies after

2 or more missed visits, the patient will be censored at the time of the latest evaluable RECIST 1.1 assessment prior to the 2 missed visits. If the patient has no evaluable visits or does not have baseline data they will be censored at Day 1 unless they die within 2 visits of baseline.

The PFS time will always be derived based on scan/assessment dates not visit dates.

RECIST 1.1 assessments/scans contributing towards a particular visit may be performed on different dates. The following rules will be applied:

- The date of progression will be determined based on the earliest of the scan dates of the component that triggered the progression for the adjudicated reviewer selecting PD or of either reviewer where both select PD as a time point response and there is no adjudication for central review (BICR) data
- For investigational assessments, the date of progression will be determined based on the earliest of the RECIST assessment/scan dates of the component that indicates progression
- When censoring a patient for PFS the patient will be censored at the latest of the dates contributing to a particular overall visit assessment.

**Note:** For target lesions, only the latest scan date is recorded in the RECIST eCRF out of all scans performed at that assessment for the target lesions and similarly for non-target lesions only the latest scan date is recorded out of all scans performed at that assessment for the non-target lesions.

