3. PRIMARY, SECONDARY AND EXPLORATORY VARIABLES

3.1 Derivation of RECIST Visit Responses

For all patients, the RECIST version 1.1 (see further Appendix F of the CSP and Independent Review Charter) tumour response data will be used to determine each patient's visit response. It will also be used to determine if and when a patient has progressed and also their best objective response.

The baseline tumour assessment is part of the screening procedures and should be performed within 0 to 42 days after the end of chemoradiation therapy and no more than 28 days before the start of study drug. For patients who are recovering from toxicities associated with prior treatment, randomisation may be delayed by up to 42 days from the end of the chemoradiation therapy.

Efficacy for all patients will be assessed by objective tumour assessments every 8 weeks (relative to the date of randomisation) for the first 12 months, then every 12 weeks thereafter, until confirmed objective disease progression as defined by RECIST 1.1 (irrespective of the reason for stopping study drug and/or subsequent therapy). For patients who discontinue study drug due to toxicity or a reason other than confirmed PD, objective tumour assessments should be continued every 8 weeks for 48 weeks (relative to the date of randomisation) then every 12 weeks thereafter until confirmed objective disease progression. If an unscheduled assessment is performed, and the patient has not progressed, every attempt should be made to perform the subsequent assessments at their scheduled visits.

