3.2.1.2 Progression free survival (PFS)

PFS (per RECIST 1.1 as assessed by BICR) will be defined as the time from the date of randomisation until the date of the first objective disease progression or death (by any cause in the absence of progression) regardless of whether the patient withdraws from randomised therapy or receives another anti-cancer therapy prior to progression (i.e., date of PFS event or censoring – date of randomisation + 1). Patients who have not progressed or died at the time of analysis will be censored at the time of the latest date of assessment from their last RECIST 1.1 assessment. However, if the patient progresses or dies after 2 or more missed visits, the patient will be censored at the time of the latest RECIST 1.1 assessment prior to the two missed visits.

Given the scheduled visit assessment scheme (ie eight-weekly for the first 48 weeks then twelve-weekly thereafter) the definition of 2 missed visits will change. If the previous RECIST assessment is less than study day 274 (ie week 39) then two missing visits will equate to 18 weeks since the previous RECIST assessment, allowing for early and late visits (ie, 2 x 8 weeks + 1 week for an early assessment + 1 week for a late assessment = 18 weeks). If the two missed visits occur over the period when the scheduled frequency of RECIST assessments changes from eight-weekly to twelve-weekly this will equate to 22 weeks (ie,

take the average of 8 and 12 weeks which gives 10 weeks and then apply same rationale hence 2×10 weeks + 1 week for an early assessment + 1 week for a late assessment = 22 weeks). The time period for the previous RECIST assessment will be from study days 274 to 344 (ie week 39 to week 49). From week 49 onwards (when the scheduling changes to twelve-weekly assessments), two missing visits will equate to 26 weeks (ie 2×12 weeks + 1 week for an early assessment + 1 week for a late assessment = 26 weeks). If the patient has no visits or does not have baseline data they will be censored at study day 1 unless they die within 2 visits of baseline (16 weeks plus 1 week allowing for a late assessment within the visit window).

The PFS time will always be derived based on scan/assessment dates not visit dates.

PFS will also be obtained using the algorithm described above for the RECIST site investigator tumour data.

RECIST 1.1 assessments/scans contributing towards a particular visit may be performed on different dates. The following rules will be applied:

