3.3.1.1 Time to symptom deterioration

For each of the symptoms scales/items in the EORTC-QLQ-C30, time to symptom deterioration will be defined as the time from randomisation until the date of the first clinically meaningful symptom deterioration (an increase in the score from baseline of ≥ 10) or death (by any cause) in the absence of a clinically meaningful symptom deterioration, regardless of whether the patient withdraws from study treatment or receives another anticancer therapy prior to symptom deterioration (i.e. date of symptom deterioration event or censoring whichever is earlier – date of randomisation + 1). Death will be included as an event only if the death occurs within 2 visits of the last PRO assessment where the symptom change could be evaluated.

Patients whose symptoms (as measured by EORTC-QLQ-C30) have not shown a clinically meaningful deterioration and who are alive at the time of the analysis will be censored at the time of their last PRO assessment where the symptom could be evaluated. Also, if symptoms deteriorate after 2 or more missed PRO assessment visits or the patient dies after 2 or more

missed PRO assessment visits, the patient will be censored at the time of the last PRO assessment where the symptom could be evaluated (prior to the two missed assessment visits). Given the scheduled visit assessment scheme (ie eight-weekly for the first 48 weeks then twelve-weekly thereafter) the definition of 2 missed visits will change. If the previous PRO assessment is less than study day 274 (ie week 39) then two missing visits will equate to 18 weeks since the previous PRO assessment, allowing for early and late visits. If the two missed visits occur over the period when the scheduled frequency of PRO assessments changes from eight-weekly to twelve-weekly this will equate to 22 weeks. The time period for the previous PRO assessment will be from study days 274 to 344 (ie week 39 to week 49). From week 49 onwards, two missing visits will equate to 26 weeks. If the patient has no evaluable visits or does not have baseline data they will be censored at day 1 unless they die within 2 visits of baseline (16 weeks plus 1 week allowing for a late assessment within the visit window).

The population for analysis of time to symptom deterioration will include a subset of the ITT population who have baseline scores ≤ 90 .

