3.3.1.2 Time to HR QoL/Function deterioration

For HR QoL/function, time to deterioration will be defined as the time from the date of randomisation until the date of the first clinically meaningful deterioration (a decrease in the function scales or the global health status/HR QoL from baseline of ≥ 10) or death (by any cause) in the absence of a clinically meaningful deterioration, regardless of whether the patient withdraws from study treatment or receives another anticancer therapy prior to HR QoL/function deterioration (i.e. date of HRQoL/function deterioration event or censoring whichever is earlier – date of randomisation + 1). Death will be included as an event only if the death occurs within 2 visits of the last PRO assessment where the HR QoL/function change could be evaluated.

Patients whose HR QoL/function (as measured by EORTC-QLQ-C30) have not shown a clinically meaningful deterioration and who are alive at the time of the analysis will be censored at the time of their last PRO assessment where the HR QoL/function could be evaluated. Also, if HR QoL/function deteriorates after 2 or more missed PRO assessment visits (using the same definitions for two missed visits as used in the ‘Time to Symptom deterioration’ derivation above) or the patient dies after 2 or more missed PRO assessment visits, the patient will be censored at the time of the last PRO assessment where the symptom could be evaluated. If the patient has no evaluable visits or does not have baseline data they will be censored at day 1 unless they die within 2 visits of baseline (16 weeks plus 1 week allowing for a late assessment within the visit window).

The population for analysis of time to HR QoL/function deterioration will include a subset of the ITT population who have baseline scores ≥ 10 .

In the analysis, RECIST 1.1 progression will not be considered as HRQoL/function deterioration and data will not be affected by RECIST progression.

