Additionally, summary statistics for the number of weeks between the time of progression and the last RECIST assessment prior to progression will be presented for each treatment group.

Summaries of the number and percentage of patients who miss two or more consecutive RECIST assessments will be presented for each treatment group.

All of the collected RECIST 1.1 data will be listed for all randomised patients. In addition, a summary of new lesions (i.e., sites of new lesions) will be produced.

Sensitivity Analyses

The following sensitivity analyses will be performed:

- Evaluation-Time bias

Sensitivity analyses will be performed to assess possible evaluation-time bias that may be introduced if scans are not performed at the protocol-scheduled timepoints. The midpoint between the time of progression and the previous RECIST assessment will be analysed using a stratified log-rank test, as described for the co-primary analysis of PFS. For patients whose death was treated as PFS event, the date of death will be used to derive the PFS time used in the analysis. This approach has been shown to be robust to even highly asymmetric assessment schedules ([Sun and Chen 2010](#)). To support this analysis, the mean of subject-level average inter-assessment times will be tabulated for each treatment. This approach will use the BICR data.

- Attrition bias

Attrition bias will be assessed by repeating the co-primary PFS analysis except that the actual PFS event times, rather than the censored times, of patients who progressed or died in the absence of progression immediately following two, or more, tumour assessments will be included. In addition, patients who take subsequent therapy prior to their last evaluable RECIST assessment or progression or death will be censored at their last assessment prior to taking the subsequent therapy. This analysis will be supported by a Kaplan-Meier plot of the time to censoring where the censoring indicator of the PFS analysis is reversed. This approach will use the BICR data.

- Ascertainment bias

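### The 22-week limit for two missed visits wrongly covers a last scan at week 48, so a PFS event after one missed scan can be censored

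*SAP*

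**What the plan says.** SAP 3.2.1.2 censors a patient at the last scan before the gap "if the patient progresses or dies after 2 or more missed visits". Protocol 11.1.3.2 has the same criterion: "2 or more missed visits, the patient will be censored at the time of the latest evaluable" RECIST assessment.

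The scan schedule in SAP 3.1 is "every 8 weeks for 48 weeks (relative to the date of randomisation) then every 12 weeks thereafter". SAP 3.2.1.2 and protocol Tables 1 and 2 agree, so scans fall at weeks 8, 16, 24, 32, 40, 48, 60, 72, 84 and so on.

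SAP 3.2.1.2 defines two missed visits by elapsed time since the last scan:

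- Last scan before day 274: 18 weeks.
- Gap spanning the change of schedule: 22 weeks, averaging one 8-week and one 12-week interval. The last-scan band is given as "The time period for the previous RECIST assessment will be from study days 274 to 344 (ie week 39 to week 49".
- Later: "From week 49 onwards (when the scheduling changes to twelve-weekly assessments), two missing visits will equate to 26 weeks".

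The band is repeated for the patient-reported deterioration endpoints in SAP 3.3.1.1 ("The time period for the previous PRO assessment will be from study days 274 to 344 (ie week 39 to week 49"). Sections 3.3.1.2 and 3.3.2.1 adopt it by reference ("using the same definitions for two missed visits as used in the" symptom derivation).

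**The concern.** The 22-week limit suits a gap made of one 8-week and one 12-week interval. Only a last scan at week 40 is followed by such a gap (weeks 48 and 60). A last scan at week 48 is followed by two 12-week intervals (weeks 60 and 72), yet days 274 to 344 place it under the 22-week limit.

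A patient who misses only week 60 and is found to have progressed at week 72 would therefore be censored back to week 48. So would a patient who missed only week 60 and died more than 22 weeks after the week-48 scan. Each has one missed visit, and the rule requires two.

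This is the derivation of a co-primary endpoint. It applies to the central-review PFS and, through the same algorithm, to the investigator PFS. Duration of response inherits the PFS dates, and APF18 is read from the PFS curve. Removing events while keeping non-events among patients who miss week 60 raises the Kaplan-Meier curve after week 48 in each arm.

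**Working it through.** **The plan's own figures.** Limit = next two scheduled intervals + 1 week early + 1 week late:

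- 8 + 8 + 1 + 1 = 18
- 8 + 12 + 1 + 1 = 22
- 12 + 12 + 1 + 1 = 26

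All three reproduce. With study day = 7 × week + 1, week 39 is day 274 and week 49 is day 344, as stated. The fault lies in which last scans receive which limit.

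**Formula applied at each visit.** Each scan has a ±7-day window. The next scan is taken as missed and the event is placed at the scan after it. All 15 × 15 = 225 date pairs are compared with the SAP limit.

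| Last scan (days) | Missed | Event at | On-time gap (weeks) | Formula limit | SAP limit | Pairs censored |
|---|---|---|---|---|---|---|
| Week 32 (218–232) | 40 | 48 | 16 | 18 | 18 | 0/225 |
| Week 40 (274–288) | 48 | 60 | 20 | 22 | 22 | 0/225 |
| **Week 48 (330–344)** | **60** | **72** | **24** | **26** | **22** | **224/225** |
| Week 60 (414–428) | 72 | 84 | 24 | 26 | 26 | 0/225 |

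Weeks 8, 16, 24, 72 and 84 also give 0 of 225. The one exception at week 48 is a scan on day 344 followed by one on day 498, exactly 154 days or 22 weeks. From an on-time week-48 scan (day 337) the limit expires on day 337 + 154 = 491 (week 70), before the week-72 window opens on day 498. A week-48 scan taken on day 345, one day outside its window, would get 26 weeks.

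**Size under the planning assumptions.** Inputs from SAP 1.3: 702 patients at 2:1 (468 and 234), PFS medians 15 and 10 months, exponential; 22-month accrual, taken as uniform. Week 48 is 11.04 months and week 72 is 16.56 months.

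- Progression-free at week 48: 234 × 0.5^(11.04/10) = 108.9 and 468 × 0.5^(11.04/15) = 281.0.
- Events in weeks 48 to 72: 34.6 + 63.3 = 97.9.
- Share with 72 weeks of follow-up at 36 months: (36 − 16.56)/22 = 0.884, giving 86.5 events. At 30 months the share is 0.611, giving 59.8.
- The documents give no miss rate. If 2%, 5% or 10% miss week 60, at most 1.7, 4.3 or 8.6 events are lost at the primary analysis, and 1.2, 3.0 or 6.0 at the interim.

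**Consequences.**

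- Power (Schoenfeld, HR 0.67, 2:1, two-sided 2.5%): √(458 × 2/9) × |ln 0.67| − 2.241 = 1.80, power 0.964. With 449 events, 0.961.
- APF18 with 10% missing: placebo 28.6% to 29.6%, MEDI4736 43.5% to 44.5%. With 2% missing, about +0.2 points in each arm.
- Simulated log-rank HR (400 trials), corrected rule against rule as written:

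| Miss week 60, placebo / MEDI4736 | Corrected | As written |
|---|---|---|
| 10% / 10% | 0.6294 | 0.6291 |
| 10% / 2% | 0.631 | 0.639 |
| 2% / 10% | 0.633 | 0.625 |

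Only the differences within a row are meaningful. The level near 0.63, against 0.667 from the medians, reflects the log-rank HR estimator applied to events tied at scan dates.

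**The case against.** The strongest reply accepts the misplaced edge and says it hardly matters. With equal miss rates the hazard ratio moves by less than 0.001. The 0.008 shift needs an imbalance that nothing in a double-blind trial with one scan schedule suggests. This stands, and the point should be presented as a small one.

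The planning model also over-produces events. With N[1 − (e^(−λa) − e^(−λb))/(22λ)], it gives 188.5 + 314.1 = 503 at 36 months (a = 14, b = 36) and 165.0 + 265.0 = 430 at 30 months (a = 8, b = 30). The plan expects 458 and 367. Scaling crudely by 458/503 and 367/430, the ranges become about 1.6 to 7.9 events at the primary analysis and 1.0 to 5.1 at the interim. The unscaled counts are therefore upper bounds on this ground too.

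The power comparison assumes a fixed analysis date. If the cut-off waits for 458 derived events, the cost is a slight delay rather than lost power. This also stands.

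Finally, the attrition sensitivity analysis in SAP 4.2.1.2 uses actual event times after missed assessments. It helps show whether the result is sensitive to the missed-visit rule. But it also restores events after genuine double misses, and in it "patients who take subsequent therapy prior to their last evaluable RECIST assessment or progression or death will be censored at their last assessment" before that therapy. It neither isolates this error nor corrects the primary PFS derivation or APF18.

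**Conclusion.** The concern holds. SAP 3.2.1.2 contradicts its own criterion at one scheduled visit: a last scan at week 48 should carry a 26-week limit and carries 22. The fault is confined to patients whose last scan was in the week-48 window, who missed week 60, and whose event fell more than 22 weeks later. Progression on an unscheduled scan, or death, within 22 weeks of the week-48 scan still counts.

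The schedule result needs no assumption beyond the documented dates and windows. The size does: it rests on the planning medians, uniform accrual and an assumed 2% to 10% missing week 60. On those terms at most about 2 to 9 of 458 events are lost, and APF18 rises by about 0.2 to 1.0 percentage points in each arm. No directional bias in the hazard ratio is shown when the arms miss scans equally. The effect on the patient-reported endpoints has not been quantified. The point should be fixed because a co-primary endpoint's written derivation is wrong, although the effect is unlikely to be material.

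**What to change.** In SAP 3.2.1.2, give the 22-week limit to a previous assessment on study days 274 to 329 and the 26-week limit from day 330 onward. Make the same change in 3.3.1.1, which carries it by reference to 3.3.1.2 and 3.3.2.1. This also removes the overlap at day 344, which as week 49 now falls under both limits. With the edge moved, no within-window date pair with one missed scan is censored after any scheduled visit checked. True double misses still are: a week-48 scan followed by an event at week 84 leaves a gap of 34 to 38 weeks.

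The protocol synopsis (Study design) says the endpoints had been met and the planned analyses concluded by Amendment 07. The correction should therefore be a supplementary PFS analysis labelled post hoc, with a listing by arm of patients whose event status changes. That replaces the assumed miss rates with an actual count. Any further PFS analysis should use the corrected limits.

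The cost is one boundary in the SAP text and program and one re-run from scan dates already held. No new data are needed.

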## **9.5 Study timetable and end of study**

If the study reaches statistical significance for PFS/OS at the interim or final analyses, additional follow-up for that particular endpoint may occur based on the needs for long term follow up with more mature data in order to estimate the long-term benefit for MEDI4736. The study will continue until all analyses for long term PFS/OS benefit are complete and those patients who have been in OS and PFS follow-up for approximately 5 years will be considered to have completed the study. Patients who have been progression free for approximately 5 years are considered cured and will no longer be considered eligible for retreatment within this protocol. Those patients who are still actively in retreatment, and continuing to receive clinical benefit, will have the option to continue on study drug on an alternate rollover or extension protocol.

The roll-over or safety extension study will ensure treatment continuation with visits and assessments per its protocol. Any patient that would be proposed to move to such study would be asked to sign a new informed consent.

The study may be terminated at individual centres once there are no longer any patients being treated or followed in progression-free or overall survival follow up or once the final DCO for the study has occurred and all queries at that centre have been resolved.

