### **9.5.1 Data collection after the primary analysis of PFS and OS**

If the study achieves statistical significance for the co-primary endpoints of PFS and/or OS at one of the planned interim analyses, then that will be considered the final analysis for that endpoint. Further analyses for that particular endpoint may still occur depending on the need to have long-term follow up or more mature data; the last DCO of the study will then be the last assessment of long-term benefit.

Patients who are receiving MEDI4736 due to re-treatment after both primary analyses of PFS and OS have been conducted may continue receiving MEDI4736 treatment, if the Investigator judges that they are gaining clinical benefit. It is recommended that the patients continue the scheduled site visits and that Investigators monitor the patient's safety laboratory results prior to and periodically during the treatment with MEDI4736 in order to manage AEs in accordance with the MEDI4736 TMGs (refer to Section 5.5.3). A summary of study procedures to be followed for patients in long-term follow up or in re-treatment (effective at the time of approval of CSP Amendment 7) is presented in [Table 11](#).

Patients in progression-free follow up will receive tumour assessment scans in accordance with [Table 11](#) (effective at the time of approval of CSP Amendment 7) up to the time of final DCO and are to undergo sampling for local laboratory assessments in such a way that continued per-protocol re treatment eligibility can be properly determined in the event of progression. Scans are to be submitted for BICR in the same manner that they were during the treatment portion of the study.

Patients in progression-free follow up and who are eligible for re-treatment (ie, patients who were randomised to the MEDI4736 arm, who completed the initial 12 months of treatment,

and who meet the eligibility criteria for re-treatment [see below]) remain eligible for possible future re treatment upon progression for up to ~5 years following their initial study randomisation if they still meet the re-treatment eligibility criteria and the Investigator judges that the patient will gain clinical benefit at that time. Patients who progress >3 years after randomisation must have a biopsy to confirm that this is a true recurrence of their original tumour and not a new primary lesion to allow for confirmation of their eligibility for re-treatment.

Eligibility criteria for re-treatment:

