**Table 9 eCRFs to be completed during long-term follow up**

Assessment to be captured	Relevant CRF page to be completed
RECIST assessments: tumour assessments should be performed relative to the date of randomisation as follows: every 26 weeks ( $\pm 4$ weeks) until confirmed PD by RECIST 1.1 by investigational site review. Please refer to Table 11 for timings of confirmatory scans.	RECIST1TLF, RECIST1NTLF, RECIST2NL, RECISTVR
Survival : every 8 weeks ( $\pm 1$ week)	SURVIVE
Statement of death	DEATH
Subsequent anti-cancer therapy	CAPRXPOST, CAPRXRPOST, CONPRO
Hospitalisations and hospital resource utilisation	HOSPAD
Specific concomitant medications for all patients regardless of treatment arm and disease status (supportive care therapy – see Table 10 )	MED
All SAEs experienced by patients whilst receiving treatment with MEDI4736 or within 90 days of discontinuing MEDI4736 must continue to be reported to the Sponsor within the usual timelines (ie, immediately, or no later than 24 hours of when the site becomes aware of the SAE; see Section 6.4.4 ). If a SAE is reported then all data relevant to the SAE (eg, concomitant medications, laboratory data, dosing data, new medical or surgical history) should be submitted as part of the SAE report	SAE

Guidelines for the management of immune-mediated reactions, infusion-related reactions, and non-immune-mediated reactions for MEDI4736 monotherapy are provided in the TMGs. The most current version of these guidelines is to be maintained within the Site Master File. In addition, a version of the current TMGs is available through the following link:

<https://tmg.azirae.com>

Please contact the Clinical Research Associate for information on how to gain access to this website.

Review of patient charts may be conducted periodically as needed by AstraZeneca or an authorised representative.

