A forest plot illustrating the hazard ratio and the corresponding 95% confidence interval will be provided to compare the primary and sensitivity analyses of progression free survival.

The effect of covariates upon the HR estimate and the consistency of treatment effect between subgroups will be analysed for PFS using the same methods as those described for OS.

A further analysis of PFS (using investigator assessed RECIST) may be performed at the time of the OS analyses, if requested by health authorities.

Time to first subsequent therapy or death (TFST)

For supportive purposes, the time to the start of subsequent therapy will be analysed using the same methodology and model as that used for the co-primary analysis of PFS. The HR for the treatment effect together with its 95% CI will be presented. In addition, a Kaplan-Meier plot of the time to the start of subsequent therapy will be presented by treatment arm and the time between progression and starting subsequent therapy will be assessed based upon the investigator data defined date of progression. This will be summarised per treatment arm but no formal comparisons will be made. No multiplicity adjustment will be applied as this is viewed as a supportive endpoint.

In patients who received a subsequent cancer therapy, a summary table of first subsequent cancer therapies by treatment arm will be provided.

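### The SAP's 26-week limit for two missed visits would censor about half of the progressions found at on-time long-term scans, which are themselves 26 weeks apart

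*SAP*

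**What the plan says.** SAP 3.2.1.2 states the rule in visits: "if the patient progresses or dies after 2 or more missed visits, the patient will be censored at the time of the latest RECIST 1.1" scan before the gap. It then converts two missed visits into weeks for an assessment scheme that is "eight-weekly for the first 48 weeks then twelve-weekly thereafter". The last of three bands reads "From week 49 onwards (when the scheduling changes to twelve-weekly assessments), two missing visits will equate to 26 weeks", and its derivation ends "1 week for an early assessment + 1 week for a late assessment = 26 weeks". This band has no end date. The same algorithm is used for investigator-assessed PFS.

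Protocol 9.5.1 sets a different schedule once the primary PFS and OS analyses are done. In Table 9, "tumour assessments should be performed relative to the date of randomisation as follows: every 26 weeks", with a window of ±4 weeks; Table 11 repeats this. The images still count: "Scans are to be submitted for BICR in the same manner that they were during the treatment portion of the study". Section 9.5 foresees their use, since "additional follow-up for that particular endpoint may occur based on the needs for long term follow up with more mature data".

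Protocol 11.1.3.2 defines the same PFS censoring in missed visits only, with no conversion to weeks. SAP 3.2.2.7 uses the two-missed-visits rule for TTDM, also without its own conversion. Neither document gives a conversion for the 26-weekly schedule.

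**The concern.** A limit meant to identify patients who dropped out of sight for two visits now equals the planned distance between two visits. A patient who attends every long-term scan, slightly early once and slightly late the next time, exceeds it.

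The censoring depends on the outcome. If a scan 30 weeks after the last one shows progression, the patient is censored at the earlier scan. If it shows none, the patient stays at risk and contributes the full interval. Late events are therefore removed selectively, and the tail of the Kaplan-Meier curve is too high in both arms. The durability of PFS is what the long-term follow-up is meant to describe.

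**Working it through.** **Reproducing the SAP's limits.** Formula: two intervals + one early window + one late window.
- 8-weekly: 2 x 8 + 1 + 1 = 18 weeks.
- Transition: 2 x 10 + 1 + 1 = 22 weeks.
- 12-weekly: 2 x 12 + 1 + 1 = 26 weeks.

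All three agree with SAP 3.2.1.2. On the 12-weekly schedule the longest on-time gap is 12 + 1 + 1 = 14 weeks, well inside 26, so the limit is sound there.

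**Long-term schedule (Tables 9 and 11: 26 weeks ±4).**
- Shortest on-time gap: 26 - 4 - 4 = 18 weeks.
- Longest on-time gap: 26 + 4 + 4 = 34 weeks.
- The SAP's own formula: 2 x 26 + 4 + 4 = 60 weeks.

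Example: scans are due at weeks 208 and 234. A patient is scanned at week 206 and at week 236, both inside the window, and the second shows progression. The gap is 30 weeks. The SAP limit censors this patient at week 206. Protocol 11.1.3.2 counts zero missed visits and keeps the event at week 236.

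**Share of on-time gaps over 26 weeks.** If the two scan dates vary independently and alike, the gap is symmetric about 26, so the share is one half less half the probability of an exact 26. Counted in whole days, it is 49.1% (uniform within ±28 days), 48.0% (normal, SD 7 days), 45.3% (normal, SD 3 days) and 46.7% (late-skewed). The SAP does not say whether exactly 26 weeks counts as two missed visits; if it does, the shares are 50.9% to 54.7%.

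**Share of progressions censored.** Longer gaps contain more events. With uniform timing, the mean excess of gaps over 26 weeks is 8/3 = 2.67 weeks, so the share is about 0.5 x 28.67 / 26 = 55%. In a simulation that includes the switch from 12- to 26-weekly scans it is about 51-52%.

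**Share of deaths censored.** A death without recorded progression is lost only if it falls beyond week 26 of the gap: 0.5 x 2.67 / 26 = 5%.

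**All late PFS events.** The assumed yearly rates of progression and death were 5% and 2%, 10% and 3%, and 15% and 5%. The simulation with the switch loses 36-39% of late events. Using 55% for progressions, with about 74% of late events being progressions (the middle case), gives 0.74 x 0.55 + 0.26 x 0.05 = 42%.

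**Effect on the curve.** Kaplan-Meier PFS from the switch, without and with the 26-week limit, 104 weeks of follow-up:

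| Progression / death per year | 1 year | 1.5 years |
|---|---|---|
| 5% / 2% | 94.5% → 96.2% | 91.2% → 94.2% |
| 10% / 3% | 90.1% → 93.4% | 84.4% → 89.9% |
| 15% / 5% | 85.1% → 89.6% | 77.0% → 84.4% |

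The rise at 1.5 years is 3.0, 5.5 and 7.4 points. With only 86 weeks of follow-up it is 3.6, 6.6 and 8.6 points. With a 60-week limit no on-time progression is censored and the curve does not move.

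**The case against.** The SAP is dated 22 March 2017, and the protocol with the 26-weekly schedule is dated 04 September 2019. By then the planned analyses were finished. The SAP introduces its conversion for the 8- then 12-weekly scheme, so one can argue that the weeks only translate a visit rule and were never meant for Table 11. That explains the mismatch but does not remove it: the band is open-ended, it is the only conversion given, and these scans still go to BICR for foreseen analyses. It does mean that the harm arises only if the conversion is carried forward. Protocol 11.1.3.2 would keep the events, so the SAP's is not the only stated derivation.

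The attrition-bias sensitivity analysis in SAP 4.2.1.2 is meant to use actual event times where the missed-visit rule censors. It mitigates in part. It is tied to the co-primary analysis, it also censors at subsequent therapy, and it is not the main estimate.

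A reader might infer that the confirmatory PFS result is compromised. It is not: Table 11 starts only after the primary PFS and OS analyses. A reader might also point to SAP 4.2.1.2, where "A further analysis of PFS (using investigator assessed RECIST) may be performed at the time of the OS analyses". That analysis depends on a health authority request and is timed at the OS analyses, before the 26-weekly scans begin, so it does not support the point. Nor do the documents show that any long-term PFS estimate has been produced with this limit.

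**Conclusion.** The point holds for long-term PFS, conditional on the SAP conversion being applied to scans on the Table 11 schedule. About half of the progressions found at on-time scans would then be censored with no visit missed, contrary to the protocol's own visit count. Roughly 36-42% of late PFS events would be lost, and the late curve would rise by about 3 to 7 points at 1.5 years in both arms.

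The one-half share needs only independent scan timing within the window; with perfectly punctual scans it would be none or all, depending on how exactly 26 weeks is treated. The size of the effect on the curve rests on assumed late rates, since the documents give none for this phase. Unscheduled scans would shorten gaps and lower all these figures. It is tempting to conclude that the comparison would favour one arm, but the rule is common to both and the direction of any hazard ratio bias cannot be derived. Interim PFS, primary PFS at 458 events, APF12 and APF18 stand as planned. TTDM is exposed if the same conversion is reused for it.

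**What to change.** Before any long-term PFS or TTDM analysis, amend SAP 3.2.1.2 and 3.2.2.7 in one of two ways:
- add a band for patients on the Table 11 schedule, with two missed visits equal to 60 weeks (2 x 26 + 4 + 4) since the last RECIST assessment; or
- drop the conversion for this phase and count missed scheduled visits directly, as protocol 11.1.3.2 does.

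For a patient whose last scan was on the 12-weekly schedule and whose next is on the 26-weekly one, use that patient's next two scheduled dates plus the 4-week window. Apply the rule to both BICR and investigator PFS.

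The cost is a short SAP addendum and one programming condition. It needs no new data or procedures, and the primary results do not change.
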